5.1.3.3 Pre-medications for Subcutaneous Injection

SC dosing cohorts will follow the same premedication guidelines as outlined in [Section 5.1.2.3](#). Additional medications for prophylaxis of CRS and/or injection site reactions, including topical medications and medications administered post-dose may be recommended based on the observed safety data in the cohorts.

5.1.3.4 Administration of Subcutaneous HPN424

HPN424 will be administered at the dose level based on the assigned cohort as outlined in [Section 3.1](#).

HPN424 will be administered once weekly (−2 days/+1 day), with a minimum of 4 non-dose days between 2 consecutive doses, via SC injection. The maximum volume per SC injection site is 1.0 mL. If multiple injections are required to deliver the assigned dose, administer at different injection sites. Injection sites should be rotated with each injection administered at a different anatomic location (i.e., upper arms, upper thighs, buttocks, or any quadrant of abdomen) than the previous injection. Do not inject into moles, scars, or areas where the skin is tender, bruised, red, hard, or not intact. Refer to the Pharmacy Manual for further instructions.

5.1.4 *Hospitalization and Monitoring*

5.1.4.1 Single Patient Cohorts and Fixed Dosing Regimen

All patients enrolled in single-patient cohorts and fixed dose 3 + 3 dose escalation arms will be hospitalized for a 48-hour (± 1 hour) observation following Cycle 1 Day 1 and Cycle 1 Day 8 dosing (administration of first 2 doses).

- If the patient experiences signs or symptoms of CRS/IRR, hospitalization may be extended for monitoring beyond 48 hours until it is confirmed that the patient is symptom free and is stable for discharge.
- If the Cycle 1 Day 1 and Cycle 1 Day 8 doses have been well tolerated, subsequent doses of HPN424 may be administered on an outpatient basis. However, even if administered on an outpatient basis, for Cycles 1, 2, and 3, patients are to remain in the clinic for safety monitoring for at least 4 hours after each HPN424 administration.
- Beginning with Cycle 4 and beyond, the observation period may be reduced to no less than 2 hours after end of HPN424 administration.

Based on emergent safety data and review by the CRC, duration of hospitalization for Cycle 1 Day 1 and Cycle 1 Day 8 may be reduced or omitted. If hospitalization is omitted, outpatient observation following the administration of the first two doses will be for at least 6 hours after the study drug administration.

In the outpatient setting, if the patient experiences signs or symptoms of CRS/IRR, post dose monitoring should be extended until it is confirmed that the patient is symptom free for at least one hour and confirmed by the treating physician that the patient is stable for discharge.

5.1.4.2 Step Dosing Regimen

For patients enrolled in the Step Dosing regimen, hospitalization is as follows:

- Priming Dose(s): Hospitalized a minimum of 48 hours after the administration of each Priming Dose.
 - If the patient experiences signs or symptoms of CRS/IRR, hospitalization may be extended for monitoring beyond 48 hours until it is confirmed that the patient is symptom free and is stable for discharge.
 - After at least 6 patients have initiated treatment with a given priming dose, duration of hospitalization for that priming dose or lower priming dose levels may be reduced or omitted based on CRC review of the safety data.
 - If hospitalization is omitted, observation following first administration of a Priming Dose will be for at least 6 hours after study drug administration.

In the outpatient setting, if the patient experiences signs or symptoms of CRS/IRR, post dose monitoring should be extended until it is confirmed that the patient is symptom free for at least one hour and confirmed by the treating physician that the patient is stable for discharge.

- Target Dose(s): Hospitalized a minimum of 48 hours after the administration of the first 2 Target Doses.
 - If the patient experiences signs or symptoms of CRS/IRR, hospitalization may be extended for monitoring beyond 48 hours until it is confirmed that the patient is symptom free and is stable for discharge.
 - If the first 2 Target Doses have been well tolerated, subsequent doses of HPN424 may be administered on an outpatient basis. During subsequent Target Doses through Cycle 3, patients are to remain in the clinic for safety monitoring for at least 4 hours after each administration. Beginning with Cycle 4 and beyond, the observation period may be reduced to no less than 2 hours after administration.

Based on emergent safety data and review by the CRC, duration of hospitalization for the first and/or second Target Dose(s) may be reduced or omitted. If hospitalization is omitted, outpatient observation following the administration of the first 2 Target Doses will be for at least 6 hours after the study drug administration.

In the outpatient setting, if the patient experiences signs or symptoms of CRS/IRR, post dose monitoring should be extended until it is confirmed that the patient is symptom free for at least an hour and confirmed by the treating physician that the patient is stable for discharge.

During Dose Expansion, hospitalization and monitoring requirements will be the same as those applied at the respective RP2D during Dose Escalation. The CRC may recommend adjustments to the observation periods based on review of cumulative safety data.

5.1.5 Storage and Stability of HPN424 and Diluent

HPN424 must be kept in a secure limited access area. HPN424 may only be used in patients enrolled specifically in this clinical study and may not be used in other persons or released to any third party, laboratory, or clinic for use in humans, or for *in vivo* or *in vitro* laboratory research, or any other use without prior authorization from Sponsor.

HPN424 vials must be stored frozen upon receipt until preparation for use; vial contents should not be shaken and should be protected from direct sunlight. Diluent must be stored refrigerated. HPN424 and diluent should not be used beyond the expiration date provided by the manufacturer. Consult the vial label, Investigator's Brochure, and Pharmacy Manual for current storage and stability conditions for HPN424 and diluent.

5.1.5.1 Drug Accountability

HPN424 will be supplied directly to the study sites. The individual receiving the shipment must verify the condition and quantity of study drug received. A drug accountability log must be maintained throughout the study to document the receipt, dispensing, return, or destruction of each vial of HPN424.

Used vials will be destroyed according to the site's policy for investigational drug destruction. Unused vials will be either destroyed at the study site or returned to the Sponsor, as agreed between each site and Sponsor. Before disposal/destruction of unused vials, final drug accountability and reconciliation must be performed by the site monitor. Documentation of destruction of vials of HPN424 must be available for review by the monitor.

5.2 **Dose-Limiting Toxicity**

Severity of adverse events (AEs) will be graded according to National Cancer Institute (NCI) Common Terminology Criteria for Adverse Events (CTCAE) version 5.0. During Dose Escalation, any of the following AEs occurring within 21 days after first administration of the Target Dose which are attributable to HPN424 and unrelated to mCRPC, intercurrent illness, or concomitant medications will be classified as DLTs:

Hematological:

- Prolonged myelosuppression, defined as CTCAE Grade ≥ 3 hematologic parameters (absolute neutrophil count [ANC] $<1000/\text{mm}^3$, platelet count $<50,000/\text{mm}^3$, or hemoglobin [Hgb] $<8 \text{ g/dL}$) in a bone marrow with $<5\%$ blasts and no evidence of leukemia or abnormal dysplasia, that lasts longer than 21 days from the point of detection
- Grade ≥ 3 neutropenia with infection
- Grade 4 neutropenia lasting >5 days
- Febrile neutropenia (defined as an ANC $<1.0 \times 10^9/\text{L}$ with a single temperature of $>38.3^\circ\text{C}$ or 101°F , or a sustained temperature of $\geq 38^\circ\text{C}$ or 100.4°F for more than one hour)
- Grade 3 thrombocytopenia with clinically significant bleeding
- Grade 4 thrombocytopenia

Non-hematological:

- Grade ≥ 3 non-hematological toxicities are considered DLTs, with the following *exceptions*:
 - Grade 3 nausea/vomiting/diarrhea or Grade 4 vomiting/diarrhea lasting < 72 hours in the absence of maximal medical therapy are NOT considered a DLT.
 - Grade 3 fatigue lasting less than 7 days is NOT considered a DLT.
 - Non-hematologic laboratory Grade 3 AE that is asymptomatic and/or rapidly reversible (returned to baseline or to Grade ≤ 1 within 7 days) unless identified as clinically relevant by the Investigator is NOT considered a DLT
 - Events of increased blood pressure are not considered DLTs if associated with symptoms of CRS/IRR and resolve in concordance with CRS symptom resolution and do not result in additional safety events.
- Dose delay or dose interruption ≥ 3 weeks is considered a DLT.
- Hy's Law (concomitant ALT or AST elevation of > 3 times the upper limit of normal [ULN] and total bilirubin elevation of $> 2 \times$ ULN without a clear alternative etiology) is considered a DLT.
- Grade 4 IRR or CRS per ASTCT ([Lee, 2019](#)), with or without pre-medication, is considered a DLT.
- Grade 3 IRR or Grade 3 CRS per ASTCT ([Lee, 2019](#)) that occurs despite a premedication regimen that includes dexamethasone is considered a DLT.

Clinically important or persistent toxicities (e.g., toxicities responsible for significant dose delay) that are not included in the above criteria may also be considered a DLT following review by the Investigators and Sponsor. To be considered a DLT, the AE must represent a clinically significant shift from baseline and must be considered to be related or suspected to be related to HPN424 by the Investigator or Sponsor.

For Step Dosing cohorts, if DLTs are observed between administration of the Priming and Target Doses, the CRC will consider the safety data of all patients treated at the Priming Dose level (including patients who received the priming dose in prior 3 + 3 cohorts and single patient cohorts) when making decisions regarding cohort expansion (e.g., expand cohort to at least 6 patients if < 6 patients have received the Priming Dose), dose escalation (or de-escalation), and priming regimen.

During Dose Escalation, patients who do not receive at least 3 Target doses of HPN424 for reasons other than DLT (e.g., logistical or technical reasons, non-DLT-related dose delays) may be considered not to be DLT-evaluable and may be replaced, but they can remain on study and receive additional treatment with HPN424 per protocol. Patients in the Dose Escalation stage who withdraw for any reason after Cycle 1 will not be replaced.

Late DLTs

Late DLTs are AEs that meet the same grading criteria as DLT criteria and occur after the DLT period through the 60-day assessment period during Dose Escalation. At the time of the CRC meetings to review a specific cohort, the late DLT events for that cohort will be reviewed by the CRC ([Section 11.9](#)), which may decide to:

- Continue enrollment in higher dose level cohorts
- Increase the number of patients at the dose level in which the late DLT occurred to satisfy the 3 + 3 decision rules. All patients will be followed for at least 60 days to reassess safety at this dose level. If the 3 + 3 decision rule of dose-escalation is reached, enrollment in higher dose level cohorts may resume. If, after the enrollment of additional patients, the CRC recommends dose de-escalation, then all patients will be dose-reduced to the recommended dose level.
- Permanently stop enrollment in higher dose level cohorts and declare the dose level to be above MTD. Increase the number of patients at the dose level in which the late DLT occurred satisfy the 3 + 3 decision rules.
- Stop the study

For any patient that is being treated at a dose level that is subsequently considered to be above the MTD, the option to dose-reduce will be discussed. If a patient tolerated the above-MTD dose level well and is benefiting (as determined by the Principal Investigator and upon consultation with the Medical Monitor), continuation of treatment at the above-MTD dose level will require re-consenting.

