All patients within a dose cohort will be observed for dose-limiting toxicities (DLTs; [Section 5.2](#)) through 21 days after the first Target Dose (i.e., the DLT observation period; [Table 15](#)). For Step Dosing cohorts, if DLTs are observed between administration of the Priming and Target Doses, the CRC will consider the safety data of all patients treated at the Priming Dose level (including patients who received the priming dose in prior 3+3 cohorts and single patient cohorts) when making decisions regarding cohort expansion (e.g., expand cohort to at least 6 patients if < 6 patients have received the Priming Dose), dose escalation (or de-escalation), and priming regimen.

Subsequent higher dose level cohorts may not be opened until all patients entered in the current dose level cohort have been treated and completed the DLT observation period, and the data have been reviewed by the CRC.

Enrollment in an arm may be stopped following review of the data by the CRC and at the Sponsor's discretion.

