7.5 Replacement of Study Patients

Patients in the Dose Escalation stage who do not receive at least 3 Target doses of HPN424 for reasons other than DLT at the Target Dose (e.g., logistical or technical reasons, non-DLT-related dose delays, or toxicity at a Priming Dose level which inhibits escalation to the Target Dose) may be replaced for DLT evaluation purposes but can remain on study and receive

additional treatment with HPN424 per protocol. Patients in Dose Escalation who withdraw for any reason after the DLT period will not be replaced.

Patients in Dose Expansion who withdraw due to documented disease progression or unacceptable treatment-related toxicity will not be replaced. Patients withdrawing for other reasons may be replaced, on a case by case basis, after discussion with the Medical Monitor.

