8.2 Treatment Period

Cycle 1 Day 1 predose assessments must be completed within 72 hours prior to the start of the Cycle 1 Day 1 dose of HPN424, unless otherwise indicated. If screening assessments were done within this window, they need not be repeated on Cycle 1 Day 1.

The timing of dose administration, hospitalization schedule ([Section 5.1.4](#)), and DLT observation period for each cohort is dependent on the assigned dosing regimen and treatment arm and detailed in [Table 15](#).

Table 15 Cycle 1 Treatment and Monitoring Schedule

	Fixed Dose Regimen	One Priming Dose Regimen (Prime A)	Two Priming Dose Regimen (Prime A + Prime B)	Three Priming Dose Regimen (Prime A + Prime B + Prime C) ^b
Priming Dose A	--	C1D1	C1D1	C1D1
Priming Dose B	--	--	C1D8	C1D8
Priming Dose C	--	--	--	C1D15
Target Dose	C1D1	C1D8	C1D15	C2D1
DLT Period	D1-D21	D1-D28	D1-D35	D1- D42
Hospitalization	C1D1, C1D8	C1D1 ^a , C1D8, C1D15	C1D1 ^a , C1D8 ^a , C1D15, C2D1	C1D1 ^a , C1D8 ^a , C1D15, C2D1, C2D8

^a Hospitalization for Priming and Target dose(s) may be reduced or omitted based on CRC review of the emergent safety data at a particular dose level (Section 5.1.4).

^b If additional Prime Doses are added (e.g., Prime Dose D) Cycle/Day for Prime Dose and first Target dose will be determined by the number of Priming doses for a given regimen (e.g., Priming Dose A will be administered on C1D1, Priming Dose B on C1D8, Priming Dose C on C1D15, and Priming Dose D on C2D1 and so on. The DLT period for all patients in a given cohort will be through 21 days after the first Target Dose.

The patient will be asked to complete scheduled visits and assessments per assigned dose regimen.

During the Treatment Period, disease assessments (including PSA and radiological imaging) are to be performed as indicated irrespective of whether treatment is delayed or missed. In other words, the schedule for these items is calendar-based and fixed relative to C1D1.

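### Two three-week DLT criteria generally cannot be established by the close of the 21-day DLT window, so they fall out of the binding 3+3 count and into discretionary late review

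*Protocol*

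**What the plan says.** Section 5.2 of the protocol defines DLTs as "any of the following AEs occurring within 21 days after first administration of the Target Dose" that are attributable to HPN424. The note to Table 15 (Section 8.2) confirms this for every regimen: "The DLT period for all patients in a given cohort will be through 21 days after the first Target Dose".

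Two criteria in the same list carry their own duration. Prolonged Grade ≥3 myelosuppression counts only if it is one "that lasts longer than 21 days from the point of detection". Separately, "Dose delay or dose interruption ≥ 3 weeks is considered a DLT". Section 5.2 does not say whether such an event is dated by its onset or by the day it reaches the required length.

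Section 3.1.1 bars a higher dose level "until all patients entered in the current dose level cohort have been treated and completed the DLT observation period" and the CRC has reviewed the data. It does not require an open event to be resolved first.

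On evaluability, Section 5.2 says that "patients who do not receive at least 3 Target doses of HPN424 for reasons other than DLT" may be treated as not DLT-evaluable and replaced. Section 7.5 words the condition as "for reasons other than DLT at the Target Dose".

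Two provisions soften this. Section 5.2 lets the Investigators and Sponsor call other events DLTs, giving "toxicities responsible for significant dose delay" as an example. Its Late DLTs paragraph has the CRC review events arising after the window, through a 60-day assessment period.

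**The concern.** A 3+3 design works by counting DLTs at a fixed decision point. A criterion that cannot be met by then does not contribute to the count, even though the protocol lists it as mandatory. Either dating convention leaves the gap. Dated by onset, the patient's status is unknown at window close. Dated by completion, the event falls outside the window and is at best a late DLT, for which one of the CRC's listed options is to carry on enrolling at higher doses.

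Holds of this kind are plausible for this drug. Table 11 holds dosing from Grade 2 upward. Section 5.4.3 reports high-grade transaminitis with HPN424, mostly after the first dose or first step increase, and asks for recovery to Grade ≤1 before redosing. Grade 3 laboratory abnormalities that cause no symptoms or reverse quickly are exempt from the DLT list unless the Investigator judges them clinically relevant. For such a patient the three-week delay rule may be the only non-discretionary criterion that applies.

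At stake is whether a higher dose opens while a candidate DLT at the current dose is still undecided.

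**Working it through.** **Inputs.** First Target Dose on day T: T = 1 (fixed), 8 (one prime), 15 (two primes), 22 (three primes), from Table 15. Weekly dosing, so later Target Doses fall due on T+7 and T+14. Nominal days are used; the −2/+1 day dosing window is ignored.

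**Reproducing Table 15.** Window close = T + 20, giving D21, D28, D35 and D42. These match the table.

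**Earliest day each criterion can be established, for events starting on or after the first Target Dose:**

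- Myelosuppression detected on day d lasts more than 21 days from d + 22.
- Delay counted from a missed second Target Dose: T + 7 + 21 = T + 28.
- Delay counted from a missed third Target Dose: T + 14 + 21 = T + 35.
- Delay counted from the first Target Dose itself, the most lenient reading: T + 21.

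| Regimen | Close | Myelosuppression detected on day T | Delay from first Target Dose | Delay from missed second dose | Delay from missed third dose |
|---|---|---|---|---|---|
| Fixed | D21 | D23 | D22 | D29 | D36 |
| One prime | D28 | D30 | D29 | D36 | D43 |
| Two primes | D35 | D37 | D36 | D43 | D50 |
| Three primes | D42 | D44 | D43 | D50 | D57 |

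Delays counted from a missed dose mature 8 or 15 days after the close in every regimen (T+28 or T+35 minus T+20). Myelosuppression in the fixed arm matures 2 days after the close if detected on D1 (23 − 21) and 22 days after if detected on D21 (21 + 22 = 43; 43 − 21 = 22).

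**Exceptions.** A delay counted from the first Target Dose is 1 day past Table 15. It ties only if the window is read as 21 elapsed days (D22 in the fixed arm). In step dosing, a cytopenia detected early in priming can be established in time: by close − 22, that is D6, D13 or D20 for one, two or three primes. A delay that begins before the first Target Dose can also mature in time. Hence *generally*, not *never*.

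**Who is affected.** If events are dated by onset, patients enrolled early in a cohort may mature before the last patient's window closes, so the gap falls mainly on the last enrolled. If events are dated by completion, it applies to every patient.

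**What one event does (Table 6).** One later-confirmed DLT moves 0/3 to 1/3 (escalate becomes expand), 1/3 to 2/3 (expand becomes stop) and 1/6 to 2/6 (escalate becomes stop). The dose that would have opened is up to 33% higher in the IV fixed arm and up to 100% higher in the step arm (Table 8).

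**The case against.** The strongest answer is that the protocol already provides for late events. If the 60 days run from Day 1, every delay in the table matures within them, as does a cytopenia detected on the last window day with up to two primes (35 + 22 = D57). On a late DLT the CRC may enlarge the cohort, stop higher-dose enrolment or declare the level above the MTD. Section 11.9 has the CRC meet whenever a DLT is identified, and Section 7.4 adds ongoing review by the Study Safety Oversight Committee (SSOC). Significant delays can be called DLTs before three weeks have passed. Exposure is also narrow, because most Grade ≥3 non-hematologic toxicity, Grade 4 thrombocytopenia, Grade 4 neutropenia beyond five days and febrile neutropenia are DLTs in their own right. The day counts run from window close, whereas CRC review takes further time, so the real gap is shorter by an unknown amount.

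All of that stands as mitigation. None of it makes escalation wait, and it replaces a binding rule with judgement. The late-DLT text is also framed by grading criteria, and a dose delay has no grade, so whether it is covered is unclear.

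A reader might go further and infer that patients held for Target-Dose toxicity could be replaced and so leave the denominator. A patient held from D8 through D21 has had one Target Dose, below the three required, and is not yet a DLT under the delay rule. But replacement is permissive, the examples in Section 5.2 are logistical, technical or non-DLT delays, and the only toxicity example in Section 7.5 is at a Priming Dose. That suggests Target-Dose holds were not meant. The text is open on this; it does not establish the stronger reading.

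**Conclusion.** The point holds. For events starting after the first Target Dose, two mandatory criteria generally cannot be established at the Table 15 close, and Section 3.1.1 allows escalation from there. They drop out of the binding 3+3 count and become at most late DLTs, where action is discretionary. The lag is 8 or 15 days for a hold counted from a missed dose, and 2 to 22 days for fixed-arm myelosuppression; a delay counted from the first Target Dose is a 1-day boundary case. This rests on nominal dosing days and on Table 15's own day count.

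The documents do not support two wider inferences. They do not show that any dose level was wrongly cleared: they give no cohort-level event data, so frequency cannot be estimated. Nor do they show that reported DLT incidence is distorted: SAP Sections 6.3 and 10 base safety analyses on all treated patients, which keeps anyone replaced.

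The sponsor decided on 10 March 2022 to discontinue during Part 1 (SAP Section 3). For this study the point bears only on how past dose-level decisions are read.

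**What to change.** In Sections 5.2, 3.1.1 and 7.5, or in a successor protocol that reuses this text:

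- Attribute both criteria by onset within the DLT period, whenever the required duration is reached.
- At window close, class a patient with an open drug-related Grade ≥3 cytopenia or a Target-Dose toxicity hold as pending: not DLT-free and, for clarity, not replaceable.
- Hold the escalation decision until the event is classified.

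The cost is wording in three sections and an occasional cohort decision delayed by about one to three weeks: up to 8 or 15 days for a hold, and up to 22 days for a cytopenia detected at the end of the fixed-arm window. Because Table 11 holds from Grade 2, some waits will be for events that resolve without becoming DLTs. How many cannot be estimated from the documents.

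For the present study, identifying late DLTs in Listing 16.2.7.3 and replaced patients in disposition Listing 16.2.1 would help a reader follow the cohort decisions. This is optional: the listings are already by patient and sorted by cohort, and a title that does not mention these items does not show that the content omits them.
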